2.2 Trial Rationale/ Justification

The aim of this 24 weeks randomized, controlled multicenter, multinational study is to investigate the effect of riociguat (MK-4836) treatment on pulmonary vascular resistance in patients with early pulmonary vascular disease, indicated by either a) mPAP ≥ 25 mmHg with PVR ≥ 2 to < 3 WU and PAWP ≤ 15 mmHg or b) mPAP 21- < 25 mmHg with PVR ≥ 2 WU and PAWP ≤ 15 mmHg.

2.3 Study Committees

The following study committees will be established, each governed by a separate charter:

- **Independent Steering Committee (SC)** - to advise on the study protocol, oversee the conduct of the study, contribute to interpretation of the results, and support publications.

Any suspension or premature termination of the study must be discussed with the SC.

3 Trial Objectives and Endpoints

3.1 Primary Objective and Primary Endpoint

- 1) To investigate the effect of treatment with riociguat (MK-4836) in patients with early pulmonary vascular disease, defined as either a) mean pulmonary arterial pressure (mPAP) ≥ 25 mmHg with pulmonary vascular resistance (PVR) ≥ 2 to < 3 WU and pulmonary arterial wedge pressure (PAWP) ≤ 15 mmHg or b) mPAP 21- < 25 mmHg with PVR ≥ 2 WU, and PAWP ≤ 15 mmHg associated with connective tissue disease (CTD) or as idiopathic/heritable form.

EudraCT: 2021-001633-40	Version 1.7 15.01.2025	ESRA
-------------------------	---------------------------	------

3.2 Secondary Objectives

- 1) To investigate, whether treatment with riociguat (MK-4836) may improve further hemodynamic and clinical parameters in patients with early pulmonary vascular disease, defined as stated above.
- 2) To assess safety and tolerability of riociguat (MK-4836) treatment in patients with early pulmonary vascular disease, defined as stated above.

Secondary efficacy endpoints will be tested hierarchically:

- change of cardiac index at rest (baseline to 24 weeks)
- change of total pulmonary resistance (baseline to 24 weeks)
- change of diffusion capacity of the lung (baseline to 24 weeks)
- change of 6-minute walking distance (baseline to 24 weeks)
- change of WHO functional class (baseline to 24 weeks)
- change in QoL (SF-36, physical summation score; baseline to 24 weeks)

Exploratory endpoints

The following parameters will be assessed in every patient according to the visits schedule and analyzed as **exploratory variables**. Secondary endpoints will be analyzed as change from baseline to 12 and to 24 weeks as exploratory variables if available according to assessment schedule.

QoL assessed by the SF-36 questionnaire

- mental summation score as well as the 8 sub scores

WHO functional class

Lung function and lung diffusing capacity

- FEV1 (forced expiratory volume in 1 second), TLC (total lung capacity), DLCO (diffusing capacity of the lung)

Echocardiography

- systolic pulmonary arterial pressure (sPAP, mmHg), right ventricular area (RV-area, cm²), and right atrial area (RA-area, cm²), tricuspid annular plane systolic excursion (TAPSE), left ventricular eccentricity index (LV-EI), RV-pump function and LV-pump function (LV-EF, %).

Analyses of blood samples

Venous blood will be analyzed to determine:

- NT-pro BNP

EudraCT: 2021-001633-40	Version 1.7 15.01.2025	ESRA
-------------------------	---------------------------	------

Blood for blood gas analyses

- oxygen partial pressure, carbon dioxide partial pressure, oxygen saturation of the blood (SpO₂), pH values, bicarbonates, base excess

Pulmonary hemodynamics by right heart catheterization

- sPAP, mPAP, diastolic pulmonary artery pressure (dPAP), pulmonary artery wedge pressure (PAWP), right atrial pressure (RAP), cardiac output and ejection fraction (CO), central venous saturation, via blood gas analysis from pulmonary artery (SvO₂)

Clinical worsening will be defined as time to first event out of:

- worsening of WHO functional class
- deterioration of 6MWD >15% compared to baseline
- need of initiation of targeted PAH treatment
- hospitalization due to worsening of right heart function
- all cause death or lung-transplantation
- atrial septostomy

Safety variables

Laboratory, electrocardiogram, vital signs, assessment of adverse events and serious adverse events will serve as safety parameters.

Patients with a serious adverse event occurring during the study treatment will be followed by the study team until the serious adverse event will have resolved to the pre-study level and/or will have been addressed according to best clinical practice.

If a patient withdraws from study treatment and agrees to stay in the study, study related examinations will be performed and data will be obtained according to protocol.

4 Trial Design

Investigator-Initiated-Trial (IIT)

This is a prospective, randomized, controlled, parallel-group, double-blind multicenter multinational clinical trial, which investigates the effect of riociguat (MK-4836) in patients with early pulmonary vascular disease, defined as either a) mean pulmonary arterial pressure (mPAP) ≥ 25 mmHg with pulmonary vascular resistance (PVR) ≥ 2 to <3 WU and pulmonary arterial wedge pressure (PAWP) ≤ 15 mmHg or b) mPAP $21\text{--}25$ mmHg with PVR ≥ 2 WU, and PAWP ≤ 15 mmHg associated with connective tissue disease (CTD) or as idiopathic/heritable form. Patients in group b will be mainly enrolled as long as patients in group a are not defined as having pulmonary arterial hypertension according to European pulmonary hypertension guidelines.

EudraCT: 2021-001633-40	Version 1.7 15.01.2025	ESRA
-------------------------	---------------------------	------

The primary efficacy endpoint in this study is the change in PVR from baseline to 24 weeks. The study consists of a pre-treatment phase of up to 28 days followed by a 24-week treatment phase. The treatment phase is divided into an 8-week titration phase, followed by a 16-week main study phase.

The patients who discontinue medication prematurely will be asked to continue with study assessments and perform study visits as outlined in the protocol. Subjects will be taking three doses daily with each dose taken 6 to 8 hours apart. In the case of side effects (e.g. symptomatic hypotension), down-titration by 0.5 mg tid is allowed. The maintenance dose achieved after 8 weeks should be at least 1.5 mg tid.

Medical examinations comprise of medical history, physical examination, electrocardiogram (ECG), blood gas analyses, lung function tests, DLCO, WHO-FC, 6MWD, quality of life questionnaires, laboratory testing (including NT-proBNP), echocardiography at rest, and right heart catheterization (RHC) according to clinical practice. If patients fulfil the inclusion criteria they will be invited to join the study. The prospective period of data collection will comprise of a 24-week study period and a follow-up phase of about 30 ± 14 days.

After the pre-treatment phase, eligible subjects will be randomized at Visit 1 in a 1:1 ratio to the following 2 treatment groups

- Riociguat (MK-4836) 1.0-2.5 mg group (titration between 1.0 mg and 2.5 mg tid based on an individual dose titration scheme)
- placebo group (placebo tid)

5 Trial Duration and Schedule

5.1 Study Phases

- Screening Phase: up to 28 days before treatment start
- Treatment phase: 24 weeks \pm 14 days including 8 weeks titration phase and 16 weeks continuation phase.
- Safety Follow-up: patient's well-being will be monitored by phone after 30 ± 14 days after last intake of study drug.

5.2 Trial Duration

The overall duration of the trial is expected to be approximately 4 $\frac{1}{2}$ years. The actual overall duration or recruitment may vary.

EudraCT: 2021-001633-40	Version 1.7 15.01.2025	ESRA
-------------------------	---------------------------	------

Total trial duration: [4 ½ years]

Duration of the double-blind phase: [24 weeks ± 14 days]

Safety follow-up: [30 ± 14 days]

5.3 Recruitment plan

Study sites will be activated to enroll the needed patient number for this study.

EudraCT: 2021-001633-40	Version 1.7 15.01.2025	ESRA
-------------------------	---------------------------	------

Case payments will be provided according to performed visits. Sites will be regularly informed about the screening process.

6 Selection of Subjects

6.1 Number of Subjects

As calculated in section 10.1, 70 subjects will be enrolled in the clinical trial, 35 subjects per treatment group.

6.2 General Criteria for Subjects' Selection

Adult male and female patients with early pulmonary vascular disease will be included.

Both an elevated mean pulmonary arterial pressure >20 mmHg and an increase of PVR >2 WU have been shown to be above the upper limit of normal and are associated with development of manifest PAH and impaired survival in CTD. As a placebo-controlled study would seem unethical in patients, who are in clear indication of targeted treatment, patients with manifest PAH according to the current definition may not be included in this study (combination of both mPAP ≥ 25 mmHg and PVR ≥ 3 WU and PAWP ≤ 15 mmHg).

It is assumed that for any patient, considered for inclusion, a regular diagnostic workup in accordance with international guidelines (ESC/ERS Guidelines) was performed. Hemodynamics will be assessed by right heart catheterization at the screening visit, up to 1 month prior to screening or up to 6 months prior to screening if the patient had no signs of clinical changes defined as change of 6MWD $>10\%$, WHO-FC change or $>30\%$ change in NT-proBNP. RHC must have been measured in the participating center under standardized conditions. For statistical considerations see section 10.

6.3 Inclusion Criteria

1. ≥ 18 years of age at time of inclusion.
2. Male and female patients with early pulmonary vascular disease, defined as either
 - a) mean pulmonary arterial pressure (mPAP) ≥ 25 mmHg with pulmonary vascular resistance (PVR) ≥ 2 to <3 WU and pulmonary arterial wedge pressure (PAWP) ≤ 15 mmHg (group I PAH according to 2022 ERS/ESC guidelines) or

EudraCT: 2021-001633-40	Version 1.7 15.01.2025	ESRA
-------------------------	---------------------------	------

b) mPAP 21-<25 mmHg with PVR ≥ 2 WU, and PAWP ≤ 15 mmHg associated with connective tissue disease (CTD) or as idiopathic/heritable form (see Group I / Nice Clinical Classification of Pulmonary Hypertension) (acc. to Simonneau et al. 2019; Humbert et al. 2022). Patients with rheumatoid arthritis or connective tissue disease of any kind, except systemic lupus erythematosus, may also be included. Patients in group b will be mainly enrolled as long as patients in group a are not defined as having pulmonary arterial hypertension according to European pulmonary hypertension guidelines.

3. Treatment naïve patients (with respect to PAH specific medication)
4. Unspecific treatments which may also be used for the treatment of pulmonary hypertension such as oral anticoagulants, diuretics, digitalis, calcium channel blockers or oxygen supplementation are permitted. Permitted are also treatments of the rheumatologic disease. However, these drugs must have been started at least 1 month before right heart catheterization.
5. Right-heart catheterization results must not be older than 1 month at Visit 1 (will be considered as baseline values, the time frame can be prolonged up to 6 months, if the patient has had no signs of clinical changes defined as >20% change of 6MWD, WHO FC, > 30% change in NT-proBNP) and must have been measured in the participating center under standardized conditions (refer to the study specific Swan Ganz catheterization manual). If the respective measurements have not been performed in context with the patient's regular diagnostic work up, they have to be performed as a part of the study during the pre-study phase (after the patient signed the informed consent).
6. Women without childbearing potential defined as postmenopausal women with amenorrhea for at least 12 consecutive months and a serum FSH level within the laboratory's reference range for postmenopausal females, women with bilateral tubal ligation, women with bilateral ovariectomy, and women with hysterectomy can be included in the study.
7. Women of childbearing potential can only be included in the study if all of the following applies (listed below):
 - a. Negative serum pregnancy test at screening and at study start (visit 1).
 - b. Agreement to undertake monthly urine pregnancy tests during the study and up to at least 30 days after study treatment discontinuation. These tests should be performed by the patient at home.
 - c. Agreement to use a highly effective contraception method from screening until at least 30 days after last dose of study medication.

EudraCT: 2021-001633-40	Version 1.7 15.01.2025	ESRA
-------------------------	---------------------------	------

Option 1 or One method from this list	Option 2	or Option 3	or Option 4
Tubal sterilization (occlusion or ligation of tubes at least 6 weeks prior to Screening)	Oral*, Implantable*, Transdermal*, or Injectable* hormonal contraceptives Intrauterine Devices	Sterilization of the male partner with documented post-vasectomy confirmation of the absence of sperm in the ejaculate PLUS one method from this list Oral*, Implantable*, Transdermal*, or Injectable* hormonal contraceptives Intrauterine devices Diaphragm, female condom cervical cap, partner's use of a condom	True abstinence from intercourse with a male partner only when this is in line with the preferred lifestyle of the subject.

* If a hormonal contraceptive is chosen from this group, it must have been taken for at least 28 days prior to study start (visit 1).

8. Patients who are able to understand and follow instructions and who are able to participate in the study for the entire period.
9. Patients must have given their written informed consent to participate in the study after having received adequate previous information and prior to any study-specific procedures.

6.4 Exclusion Criteria

1. Patients with systemic lupus erythematosus.
2. Concomitant PAH-targeted treatment is not allowed during the study. Accordingly, patients scheduled to receive another investigational drug during the course of this study cannot participate (see exclusion criterion 12). Patients already receiving or having received any PAH targeted therapy will therefore not be included into the study. Such treatment may not be discontinued to enable inclusion into the study.
3. Concomitant treatment with phosphodiesterase 5 inhibitors, endothelin receptor antagonists and prostacyclin analogues due to digital ulcers is contraindicated and must not

EudraCT: 2021-001633-40	Version 1.7 15.01.2025	ESRA
-------------------------	---------------------------	------

be taken during the study period. Such drugs must have a washout-phase of 3 days at the time of right heart catheterization at screening. Intravenous treatment with prostacyclin analogues should not be performed within 1 week of right heart catheterization. Any decision to discontinue above-mentioned drugs will be made by the clinicians and the patient at screening, which takes part during the patients' regular routine visit. The discontinuation of above-mentioned drugs will be evaluated by considering the presence or absence of digital ulcers and their frequency of appearance in the patient's medical history.

4. Pulmonary hypertension explained by other cause including group 2, 3, 4 and 5 PH according to the current guidelines.
5. Cardiac comorbidity, defined with three or more of the following conditions: uncontrolled arterial hypertension, diabetes mellitus, body mass index >35 , left atrial enlargement >20 cm 2 , atrial fibrillation, left ventricular ejection fraction $<50\%$.
6. Pulmonary comorbidity, defined as forced vital capacity (FVC) ≤ 70 ; forced expiratory volume in 1 second (FEV1) $\leq 50\%$; diffusion capacity of the lung (DLCO) $\leq 30\%$.
7. Patients with a medical disorder, condition, or history of such that would impair the patient's ability to participate or complete this study in the opinion of the investigator.
8. Patients with underlying medical disorders with an anticipated life expectancy below 2 years (e.g. active cancer disease with localized and/or metastasized tumor mass).
9. Patients with a history of severe or multiple drug allergies (defined as allergic reactions to three or more structurally unrelated drugs).
10. Patients with hypersensitivity to the investigational drug or any of the excipients.
11. Contraindications according to summary of product characteristics of riociguat (e.g. arterial hypotension with systolic blood pressure <95 mmHg; nitrates or nitric oxide donors (such as amyl nitrite) in any form including recreational drugs)
12. Participation in any clinical drug trial within 4 weeks prior or 5 half-lives, whichever longer, to screening of this study and/or patient, who is scheduled to receive an investigational medicinal product (IMP) during the course of this study
13. Background therapy with highly anti-fibrotic drugs (pirfenidone) or nintedanib, prednisolone >10 mg/day

EudraCT: 2021-001633-40	Version 1.7 15.01.2025	ESRA
-------------------------	---------------------------	------

6.5 Criteria for Removal or Withdrawal

6.5.1 Withdrawal of Subjects

A subject will be withdrawn from the trial treatment for the following reasons:

1. at their own request or at request of their legal representative
2. if, in the investigator's opinion, continuation of the trial would be detrimental to the subject's well-being
3. occurrence of a severe serious adverse event (SAE) caused by the IMP
4. The participant has a medical condition or personal circumstance which, in the opinion of the investigator placed the participant at unnecessary risk from continued administration of study treatment. This includes progression or aggravation of the pulmonary hypertension, so that appropriate PAH targeted therapy may be introduced without delay.
5. The participant has a confirmed positive serum pregnancy test.

The Coordinating Investigator decides about withdrawal of subjects from trial treatment in case of occurrence of criteria mentioned above.

Patients with a serious adverse event occurring during the study treatment will be followed by the study team until the serious adverse event will have resolved to the pre-study level and/or will have been addressed according to best clinical practice. The patient, either willingly withdrawn from the study or due to premature termination, will be asked thoroughly to complete all examinations scheduled for the final trial day, and these will be performed as far as possible and documented.

In all cases, the reason for withdrawal must be recorded in the CRF and in the subject's medical records.

In case of withdrawal of a subject at his/ her own request, the reason should be asked for as extensively as possible and documented.

All efforts will be made to follow up the subject.

A subject may/ will be withdrawn from all trial related procedures (including follow-up visits) for the following reasons:

- at his/her own request or at request of his/her legal representative
- non-adherence to the trial-related requirements, which may (have) influence(d) the validity of the trial data

EudraCT: 2021-001633-40	Version 1.7 15.01.2025	ESRA
-------------------------	---------------------------	------

6.5.2 Replacement of Subjects

Per treatment arm, 35 subjects will be enrolled and included into the modified intention to treat (ITT) and safety analysis (SA) (total n=70). Subjects who terminate the study prematurely will not be replaced as a 15% drop-out rate is included in this sample size calculation.

6.5.3 Premature Closure of the Clinical Trial

The trial can be prematurely closed or suspended by the Coordinating Investigator in case if new serious risks for subjects become known. The Ethics Committee (EC) and the competent regulatory authorities must then be informed. Furthermore, the Ethics Committee(s) and competent regulatory authorities themselves may decide to stop or suspend the trial.

Should the trial be closed prematurely, all trial material (completed, partially completed, and blank CRF, randomization envelopes, IMP, etc.) must be returned to and/or kept within the files of the Coordinating Investigator.

All involved investigators have to be informed immediately about a cessation/ suspension of the trial. The decision is binding to all trial centers and investigators.

6.6 Prior and Concomitant Illnesses

Relevant additional illnesses present at the time of informed consent are regarded as concomitant illnesses and will be documented on the appropriate pages of the CRF as medical history. Included are conditions that are seasonal, cyclic, or intermittent (e.g. seasonal allergies; intermittent headache).

Abnormalities which appear for the first time or worsen (intensity, frequency) during the trial are adverse events (AEs) and must be documented on the appropriate pages of the CRF.

6.7 Prior and Concomitant Treatments

Any prior or concomitant therapy must be assessed in terms of potential interactions with the study drug as listed in the most current version of the riociguat summary of product characteristics. Relevant additional treatments administered to the subjects on entry to the trial or at any time during the trial are regarded as concomitant treatments and must be documented on the appropriate pages of the CRF.

In case of clinical worsening and if clinically indicated additional PAH-targeted rescue medication will be initiated at the discretion of the investigators. If patients present with manifest PAH after 24 weeks at the end of the double-blind phase, patients will be offered targeted treatment according to current PH guidelines. Participants will not be included if scheduled to receive another investigational drug during the course of this study.

EudraCT: 2021-001633-40	Version 1.7 15.01.2025	ESRA
-------------------------	---------------------------	------

Patients receiving highly anti-fibrotic drugs (pirfenidon), nintedanib, prednisolone >10 mg/day or any other PAH specific treatment may not participate in this study. Sildenafil and tadalafil must be discontinued at least 24 hours and at least 48 hours respectively prior to first administration of riociguat. Moreover, administration of concomitant drugs that may decrease riociguat plasma concentration as listed in the current summary of product characteristics should be avoided (e.g. strong CYP3A4 inducers).

7 Investigational Medicinal Product

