Riociguat (MK-4836) dose will be individually adjusted in accordance with the in-label titration regimen. Dose adjustment will be performed every two weeks by phone taking the systemic blood pressure of the patient, the subjects and physicians' subjective estimation and occurrence of adverse reactions into account. At week 8 the maintenance dose will be established and furtherly continued for the rest of the study.

Interim Visit / Visit 2 (week 12)

At the interim visit in week 12 assessments from screening /baseline will be repeated (except RHC and medical history) as described in Section “8.1 Overview of visits and assessments”. Unused study drug will be collected and medication for the remaining 12 weeks at maintenance dose will be supplied.

Termination visit / Visit 3 (week 24)

At this visit in week 24 assessments will be conducted as described in Section “8.1 Overview of visits and assessments”.

Follow-up / Visit 4 (30 days after last study drug intake)

Phone call 30±14 days after last study drug intake to assess adverse events and record a final pregnancy test (WOCBP only).

[figure not shown]
Excluded medication:

Pirfenidon; nintedanib, prednisolone >10 mg/day, PAH specific treatment

EudraCT: 2021-001633-40	Version 1.7 15.01.2025	ESRA
-------------------------	---------------------------	------

Pre-treatment period:	N/A
Duration of observation	Up to 28 days screening period, 24 weeks double-blind, controlled study phase, + 30 days follow-up
Follow-up period	30 days after week 24 visit each patient performs a follow-up visit via phone. Clinical follow-up of all SAEs until they have been resolved or improved if possible.
Clinic visits	Double-blind: Screening visit, baseline visit, week 12 and week 24 Additional titration visits every two weeks via phone in the double-blind study phase (week 2, 4, 6, 8), and phone follow-up 30 days after last study drug intake.
Dosing regimen	Individual adjustment during the 8 weeks titration period according to the in-label titration regimen
Route of administration	Oral riociguat (MK-4836) or respective placebo
Endpoints	All endpoints will be compared riociguat (MK-4836) vs. placebo:
Primary	Pulmonary vascular resistance, change from baseline to 24 weeks

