9.6 Emergency Treatment

During and following a subject's participation in the trial, the investigator should ensure that adequate medical care is provided to a subject for any AE including clinically significant laboratory values. The investigator should inform a subject when medical care is needed for intercurrent illness(es) of which the investigator becomes aware.

In case of clinical worsening and if clinically indicated additional PAH-targeted rescue medication will be initiated.

10 Statistical Procedures

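### The protocol's rules for PAH-targeted rescue in a patient who worsens on blinded treatment conflict, and a PVR measured after rescue enters the primary analysis unmarked

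*Protocol*

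**What the plan says.** Five places in the protocol bear on the same event.

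- **6.7 Prior and Concomitant Treatments:** "In case of clinical worsening and if clinically indicated additional PAH-targeted rescue medication will be initiated at the discretion of the investigators".
- **9.6 Emergency Treatment:** "In case of clinical worsening and if clinically indicated additional PAH-targeted rescue medication will be initiated". This sentence does not say who decides.
- **6.4, exclusion criterion 2:** "Concomitant PAH-targeted treatment is not allowed during the study". No exception for rescue is stated.
- **Synopsis, excluded medication:** "Pirfenidon; nintedanib, prednisolone >10 mg/day, PAH specific treatment".
- **6.5.1, withdrawal reason 4:** the subject will be withdrawn from trial treatment for a medical condition that puts them at unnecessary risk. "This includes progression or aggravation of the pulmonary hypertension, so that appropriate PAH targeted therapy may be introduced without delay". On who decides: "The Coordinating Investigator decides about withdrawal of subjects from trial treatment in case of occurrence of criteria mentioned above".

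Two further passages are relevant. Section 6.7 sets minimum gaps of 24 hours for sildenafil and 48 hours for tadalafil, but only before the first riociguat dose. Criterion 3 of 6.4 says: "Concomitant treatment with phosphodiesterase 5 inhibitors, endothelin receptor antagonists and prostacyclin analogues due to digital ulcers is contraindicated".

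On the analysis side, Protocol 3.2 and section 4 ask patients who stop study drug to continue with assessments. SAP 1.3 and section 8 include the final assessments of patients who stop early. Protocol 10.3.1 and SAP 7.5 make the primary analysis a complete-case ANCOVA of the change in PVR. Neither document says how a PVR measured after rescue is handled.

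**The concern.** A site whose patient worsens between baseline and week 24 finds three instructions that do not refer to one another: start additional therapy, do not give that therapy during the study, or withdraw the patient first. They differ on whether study drug stops and on who decides. The event matters for safety, because hypotension is a listed side effect (7.4) and the protocol already separates two phosphodiesterase 5 inhibitors from the first riociguat dose.

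The second issue concerns the estimate. A PVR taken after rescue reflects the rescue drug as well as the assigned treatment. Including it may be a legitimate choice, but the plan does not state it as one, and the reader of the results could not tell how many values were affected.

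**Working it through.** **1. The rules side by side**

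| Question | 6.7 and 9.6 | 6.4 criterion 2 and synopsis | 6.5.1 reason 4 |
|---|---|---|---|
| May PAH-targeted therapy start during the study? | Yes, on worsening if clinically indicated | No, with no exception | Yes, as the purpose of withdrawal from trial treatment |
| Does study drug stop? | Not stated | Not addressed | Yes |
| Who decides? | Investigators (6.7); not stated (9.6) | Not addressed | Coordinating Investigator |
| Interval between riociguat and rescue? | Only for sildenafil and tadalafil before first riociguat | Not addressed | Not stated |

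The first row is a direct conflict. The second and third rows give different or missing answers, and nothing ranks the sections.

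**2. Does a PVR after rescue reach the primary analysis?**

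- If study drug continues alongside rescue, the patient stays in the trial and has right heart catheterization at week 24 (8.1). The value is a complete case.
- If the patient is withdrawn from trial treatment first, 3.2 and section 4 still ask for study assessments, 6.5.1 asks for the examinations of the final trial day, and SAP 1.3 and section 8 include the results. A PVR obtained this way is also a complete case.

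The value therefore enters under either reading. The missing-data and outlier rules (SAP 6.1 and 6.2) do not address it. The per-protocol set does not clearly remove it, because the listed major deviations are unmet inclusion criteria and study drug not given according to protocol (Protocol 10.2, SAP 2.1). Rescue is not named.

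**3. Size per rescued patient**

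Inputs:
- 35 patients in total (SAP section 3). Assumption: an even split, so about 17 per arm.
- Extra fall in PVR after rescue. Assumption: equal to the EDITA difference. From Protocol 10.1, 0.02 − (−0.59) = 0.61 WU, which reproduces the tabulated 0.61.
- Rescue rate: not given in either document.

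Shift in arm mean = k × 0.61 / n, for k rescued patients among n analysed.

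| k | n = 17 | n = 14 |
|---|---|---|
| 1 | 0.036 WU | 0.044 WU |
| 2 | 0.072 WU | 0.087 WU |
| 3 | 0.108 WU | 0.131 WU |

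The n = 14 column applies the planned 15% dropout (17 × 0.85 = 14.45, taken as 14). With n = 17, one patient's shift is 1/17 = 5.9% of an EDITA-sized difference. If rescue is more common on placebo, the observed difference shrinks. If it is more common on riociguat, the difference grows.

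**The case against.** A coherent reading exists: withdraw under 6.5.1, then rescue under 6.7, so that nothing is concomitant with study drug. Criterion 2 is also an entry criterion, and its other sentences concern who may be included. This reading is plausible, but 6.7 and 9.6 do not state it, and criterion 2 speaks of the whole study, in which patients off study drug are asked to remain.

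Several stronger readings are tempting, and the documents do not support them.

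- *Sites are told to combine drugs the protocol calls contraindicated.* Criterion 3 ties that word to use for digital ulcers. For PAH use the wording is that of criterion 2.
- *Study drug continues during rescue.* This is inferred from the word additional and the absence of a stopping rule. No passage says it.
- *Sites must act without safeguards or knowledge of the arm.* Section 6.7 requires an interaction check against the current product information, criterion 11 excludes patients with contraindications listed there, and 7.7 and 9.5 allow emergency unblinding when medically imperative.
- *Every patient with clinical worsening is affected.* Rescue also requires a clinical indication.
- *The data are not collected.* Concomitant medication is scheduled at every visit (8.1), and dose adjustments and interruptions are recorded (7.5).

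It is also fair to say that the shift per patient is small, that it borrows an ambrisentan result, and that in the likelier direction it works against finding an effect. SAP sections 3 and 8 report that the trial stopped early with 35 patients, so new protocol wording may protect few or no current patients. These points limit the size of the problem. They do not establish which rule governs, and they do not identify the affected PVR values.

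**Conclusion.** The point stands as a conflict between stated rules on a safety-relevant event, together with an unstated choice in the primary analysis. The first part rests on the text alone. The second holds whether or not study drug stops when rescue starts. Its size cannot be fixed without the rescue rate: about 0.036 WU per rescued patient, assuming 17 per arm and an extra fall of 0.61 WU, and somewhat more if fewer patients have complete data. The documents do not show that any patient received rescue, that riociguat was combined with another PAH drug, or that the primary result is biased. No view is taken here on which clinical rule is right.

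**What to change.** **Protocol.** Reconcile the synopsis list of excluded medication, 6.4 (criterion 2, and criterion 3 where it bears on the same classes), 6.5.1 reason 4, 6.7 and 9.6 into one cross-referenced rule. It should state what happens to study drug when PAH-targeted rescue starts, what applies to the interval in that direction, and who decides. The sponsor must choose the clinical content. The cost is wording only. With recruitment ended, the gain is mainly a clear record of the rule sites were working under, and a sound text if the protocol is reused.

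**SAP.** Before unblinding, use the concomitant-medication and exposure records already collected to flag any PVR measured after the start of PAH-targeted rescue. State that the primary analysis includes these values, report their number by arm, and repeat the primary ANCOVA without them. This assumes that the records carry usable start dates, which should be confirmed first.

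The cost is one extra table. Excluding values after rescue conditions on an event that occurs after randomisation and may depend on treatment, so the result should remain a sensitivity analysis and not replace the primary one.
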